#### **4.0 Human Subjects**

##### **4.1 General Characteristics**

We intend to enroll 164 participants, 92 older veterans, and a maximum of 72 study partners for participation in the study.

##### **4.2 Inclusion of Vulnerable Subjects and Special Populations**

N/A

##### **4.3 Inclusion of Incompetent Subjects**

N/A

##### **4.4 Inclusion/Exclusion Criteria**

###### **a. Bedford AgeWISE Course (Veterans)**

Inclusion Criteria: VETERANS: Veterans > 50 years old with subjective cognitive complaints who want to learn more about cognitive aging; English speaking as all intervention materials are written in English.

Exclusion Criteria: VETERANS:

Veterans with impairment on a cognitive screening measure, as determined using age corrected criteria (using criteria: Schretlen, Testa, and Pearlson, 2010) as follows:

Age / MMSE Cut-off

51-55 / 26 and below

56-60 / 25 and below

61-65 / 25 and below

66-70 / 25 and below

71-76 / 23 and below

76-80 / 23 and below

81-85 / 23 and below

86 + / 22 and below

Or self or informant reported diagnosis of a brain disorder affecting cognition such as Alzheimer's disease, Mild Cognitive Impairment, Parkinson's disease, other dementia, stroke, or brain injury or diagnosis of a major mental illness such as major depression, schizophrenia, or bipolar disorder; active alcohol or substance abuse.

Inclusion Criteria: STUDY PARTNER: Study partners will be identified by eligible veterans. Study partners can include spouses or significant others/partners, adult children, or other family members. Study partners must be 18 years of age or older. Study partners must have at least 10 hours per week of direct contact (in-person) with the veteran. Study partners must be English speaking as all materials are in English.

Exclusion Criteria: STUDY PARTNER: Study partners must not be diagnosed with a brain disorder affecting cognition such as Alzheimer's disease, Mild Cognitive Impairment, Parkinson's disease, other dementia, stroke, or brain injury or diagnosis of a major mental illness such as major depression, schizophrenia, or bipolar disorder; active alcohol or substance abuse, as indicated by self- and veteran-report.

###### **b. Bedford AgeWISE Course (Non-Veterans)**

Inclusion Criteria: NON-VETERANS:

Non-Veteran > 50 years old with subjective cognitive complaints who want to learn more about cognitive aging; English speaking as all intervention materials are written in English.

Exclusion Criteria: Non-Veterans:

Non-Veterans with impairment on a cognitive screening measure, as determined using age corrected criteria (using criteria: Schretlen, Testa, and Pearlson, 2010) as follows:

Age / MMSE Cut-off

51-55 / 26 and below

56-60 / 25 and below

61-65 / 25 and below

66-70 / 25 and below

71-76 / 23 and below

76-80 / 23 and below

81-85 / 23 and below

86 + / 22 and below

Or self or informant reported diagnosis of a brain disorder affecting cognition such as Alzheimer's disease, Mild Cognitive Impairment, Parkinson's disease, other dementia, stroke, or brain injury or diagnosis of a major mental illness such as major depression, schizophrenia, or bipolar disorder; active alcohol or substance abuse.

c. Telemental Health AgeWISE Course

Inclusion Criteria: Veterans > 50 years old with subjective cognitive complaints who want to learn more about cognitive aging; English speaking as all intervention materials are written in English.

Exclusion Criteria: N/A

#### 4.5 Recruitment Procedures

##### Bedford AgeWISE Course:

Healthy veterans ages 50 to 90 will be recruited from the VA. Veterans will be recruited through flyers posted around the hospital. Veterans will also be recruited through the Neuropsychology Service by being provided with a flyer about the study when they appear to be an appropriate study candidate; interested veterans would then be able to call study staff on their own and express interest. Veterans will also be recruited through local Veterans of Foreign Wars Posts, American Legion Posts, and Councils On Aging. Flyers will be provided to staff at these locations and recruitment protocol, determined by each location, will be followed for recruitment procedures. Enrolled veterans will be asked if they have a study partner that meets inclusion/exclusion criteria that they would like to participate. If a study partner is identified the veteran will be given a flyer to pass along to their potential study partner and the study partner will be responsible for contacting study staff if they agree able to learning about the study.

##### Qualitative Interview

Veteran cohort: Veterans randomly assigned to Group B will be offered the opportunity to participate in a qualitative interview. If Veterans decline to participate in the qualitative interview, this will not affect their participation in the rest of the study.

Veterans assigned to Group B who were enrolled in the study prior to the implementation of the qualitative interview portion of the study (and are still enrolled) will be provided the opportunity to participate in the qualitative interview. Study staff will contact each Veteran, assigned to group B, via telephone to inquire if they are interested in participating in the qualitative interview. During this time of contact Veterans will be informed that their participation in the study as a whole will not be affected by their decision to participate or not participate in the qualitative interview portion of the study.

Non-Veteran cohort: Non-Veterans will be recruited from Councils on Aging, libraries, and other public spaces. Flyers will be provided to staff at these locations and recruitment protocol, determined by each location, will be followed for recruitment procedures.

## Telemental Health AgeWISE Course

Veterans participating in the Telemental Health AgeWISE course will be recruited to participate in the research study via flyers that will be provided to staff at VA Community Based Outpatient Clinics; interested veterans would then be able to call study staff on their own and express interest.

**4.5.1 Subject Identification and Pre-Enrollment Screening:** Subjects will be identified by providers.

**4.5.1a HIPAA Authorization for Screening:**  
Bedford AgeWISE course subjects will sign a freestanding authorization form.

**4.5.1b Consent to Screening:**  
Bedford AgeWISE course subjects will sign a screening ICF.

**4.5.2 Enrollment:** Enrollment is the responsibility of the research team approved by the IRB.

**4.5.2a HIPAA Authorization:**  
Bedford AgeWISE course and Telemental Health AgeWISE course subjects will sign a freestanding authorization form.

**4.5.2b Informed Consent:**  
Bedford AgeWISE course and Telemental Health AgeWISE course subjects will sign an ICF.

**4.5.2c Audio-Video Consent:**  
Subjects recruited for the qualitative interview will sign an Audio-Video Consent form.

## 4.6 Risk/Benefit Ratio

### 4.6.1 Potential Risks and Methods to be Used to Minimize Risks:

There is a small risk that something about veterans from this study will become known to others. We will store data collection forms separate from signed consent forms and other identifying information. All study forms will be stored in locked cabinets. All electronic data will be stored on password protected computers. The code linking the study number on data collection forms and information that can identify subjects is stored in a separate password protected computer. See the confidentiality section for more information.

Other than a potential breach of confidentiality, there are no known risks for subjects participating in this study. Veterans will be immediately informed of any new findings during the course of the study that would influence their participation, including any information about unforeseen risks that arise. There are minimal potential discomforts and these include feeling frustrated or uncomfortable when completing study measures. Every effort will be made to minimize such discomforts. Veterans will be free to discontinue their participation at any time. During assessments, all instruments will be carefully explained.

### 4.6.2 Data and Safety Management Plan:

#### 4.6.2.1 Data Security

In order to maintain the confidentiality of all veterans, informed consent forms and research data will be kept in two separate folders, in separate locked filing cabinets. Informed consent forms will not be included in the medical record. Identifiable information, such as the veteran's consent form, medical history, and reimbursement form (which contains their address and social security number) will be placed in an identifiable folder and placed in a locked filing cabinet. All veterans will be assigned codes and a folder will be made with their research code

on it and all study data will be placed in these folders with only the research code on it. The research data will be placed in a separate locked filing cabinet from the identifiable information. The only people who will have access to this identifiable information will be the Principal Investigator and the research study staff. Identifiable information will be kept in folders in one locked filing cabinet on the Bedford Veterans Hospital campus. Research data will be kept in folders with the participant's code on it in another (separate) filing cabinet and the database that links the identifiable information and the research codes will only be able to be accessed by the PI and research coordinator.

#### **4.6.2.2 Data Safety Monitoring**

The Principal Investigator and the research coordinator will be responsible for reporting Adverse Events to the IRB and, when required, to ORO, ORD, and other Federal Agencies or Sponsors.

**4.6.3 Potential Benefits:** There may be direct benefits to those participating including an increase of knowledge about memory aging, improved psychological wellness, and improved cognitive and functional ability, but this has yet to be shown and it is possible that there will be no direct benefit to participants or limited benefit. Benefits to the veteran population include increased knowledge about interventions that help to improve the odds of successful cognitive aging.

**4.6.4 Alternative Procedures:** There are no alternatives to participation. You may choose not to participate in this study.

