### 3.2 Type of Study

Prospective, randomized, no treatment control

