#### b. Study Related Procedures

- i. Bedford AgeWISE Course: The memory and aging course will take place in the building 5 solarium on the Bedford VA campus. The course will be run by neuropsychology staff under the supervision of [name] [name], a clinical neuropsychologist who has developed this manualized group, and has run the group for a number of years at the Bedford VA. Healthy older adults ages 50 to 90 will be recruited from the community at large and from advertisements on the Internet and local gathering places. Over the next year, we intend to enroll a maximum of 144 participants. Of the 144 participants, 72 of those will be older veterans, and 72 will be study partners, when study partners are identified, available, and willing to participate. Veterans without study partners will not be excluded from the study. Of the 72 veterans (with or without study partners), 36 will be assigned to the intervention group and 36 will be assigned to the control group. All veterans participating in the study will perform a standard battery of neuropsychological tests(attached). These tests will be administered in a separate study session. Veterans will be excluded if they display impairment on a cognitive screening measure, as determined using age corrected criteria (using criteria: Schretlen, Testa, and Pearlson, 2010) as follows:

Age / MMSE Cut-off

51-55 / 26 and below

56-60 / 25 and below

61-65 / 25 and below

66-70 / 25 and below

71-76 / 23 and below

76-80 / 23 and below

81-85 / 23 and below

86 + / 22 and below

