a. Qualitative Interview with Bedford AgeWISE Cohort: A portion of the Veteran participants randomly assigned to the Group B condition of the study will be recruited to participate in qualitative interviews about their perceptions of memory and aging. A non-veteran cohort will also be recruited for this portion to differentiate between Veteran-specific concerns and cognitive aging. The qualitative interviews will be audio-recorded for the purpose of maintaining accurate records and interpretation of Veteran responses to questions asked during the interview. Interviews will be recorded using the audio-recording function of VA issued webcams. The video function of these webcams will not be used. These audio recordings will only be obtained for research analysis and will not be disclosed beyond the VA.

- ii. Telemental Health AgeWISE Course: This version of the AgeWISE course will be taught via the Telemental Health Service from the ENRM Bedford VA campus. Veteran participants will view the Telemental Health AgeWISE course at Community Based Outpatient Clinics. Veterans ages 50-90 will be recruited from the Telemental Health AgeWISE course. Over the next year, we intend to enroll 20 participants for this portion of the study. All Veterans participating in the Telemental Health AgeWISE course will be provided with questionnaires prior to and immediately after the 12-week course. There will be no participant screening for this portion of the study. This portion of the study will seek to understand the perceived impact of the memory and aging course on participants. Thus, no cognitive restrictions must be met. There will be no randomization for this portion of the study.

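### Section 4.4(a) does not exclude veterans who have already taken AgeWISE, and nothing stops or records no-treatment controls taking it elsewhere, so the arms could be diluted unseen

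*Combined protocol and SAP*

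**What the plan says.** **The comparison.** Section 3.2 describes the design as "Prospective, randomized, no treatment control". Section 3.3(b)(i) adds that "36 will be assigned to the intervention group and 36 will be assigned to the control group". Veterans are assessed at baseline, within two weeks after the intervention, and six months after that.

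**The course before the trial.** Section 2.2 says the intervention was designed as a clinical service and refined over four years. Section 3.3(b)(i) says neuropsychology staff run it under a neuropsychologist who "has run the group for a number of years at the Bedford VA".

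**Who may be randomised.** Section 4.4(a) admits English-speaking veterans over 50 with subjective cognitive complaints and an interest in learning about cognitive aging. The exclusions are impairment on the cognitive screen, a brain disorder, major mental illness, and active alcohol or substance abuse. Earlier AgeWISE attendance is not mentioned. Section 4.5 lists the Neuropsychology Service among the recruitment sources.

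**The other route to the course.** Section 3.3(b)(ii) says: "This version of the AgeWISE course will be taught via the Telemental Health Service from the ENRM Bedford VA campus". It is viewed at outpatient clinics and lasts 12 weeks. The same section says "There will be no participant screening for this portion of the study", and Section 4.4(c) lists no exclusions. On recruitment, Section 3.3(b)(ii) says "Veterans ages 50-90 will be recruited from the Telemental Health AgeWISE course", and Section 4.5 says "Veterans participating in the Telemental Health AgeWISE course will be recruited to participate in the research study via flyers".

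**Measurement and analysis.** The measures and interviews in Sections 3.3 and 3.4 include no item on AgeWISE attendance outside the assigned arm. Section 3.5 plans a group-by-time repeated measures ANOVA and does not mention exposure. Section 4.6.4 states: "There are no alternatives to participation".

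**The concern.** A no-treatment comparison is informative only if controls do not receive the treatment and participants in both arms still have it to gain. The rules as written protect neither condition.

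- **Earlier attendance.** A veteran who took the clinical course can be randomised to either arm. If the course teaches durable knowledge and strategies, that veteran has less left to gain when assigned to it.
- **Attendance during follow-up.** A control meets the Telemental criteria as written, because Section 4.4(c) repeats the inclusion conditions of Section 4.4(a) and adds no exclusions. Trial recruits are selected for wanting to learn about the topic, so a control has a motive to look for the course.

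Both exposures act in the same direction: they shrink the group-by-time contrast. A null result could then mean an ineffective course or a contaminated comparison. With attendance unrecorded, the data could not tell these apart.

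**Working it through.** **1. Plan's own figure.** There is none to reproduce. The documents give no effect size, SD, alpha, power or crossover rate. The enrolment counts agree: 36 + 36 = 72 randomised veterans; 72 + 72 study partners = 144; 72 + 20 Telemental veterans = 92; 92 + 72 = 164, as in Section 4.1.

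**2. Can a prior attendee be randomised?** The course ran for years at this site (Sections 2.2 and 3.3(b)(i)). Neuropsychology staff run it, and the trial recruits through the Neuropsychology Service (Section 4.5). None of the exclusions in Section 4.4(a) concerns earlier attendance. So yes, under the written rules.

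**3. Can a control take the course before the last assessment?** Sections 3.3(b)(ii) and 4.4(c) would admit one. The follow-up window is 12 weeks, plus up to 2 weeks, plus 6 months, or roughly nine months. A 12-week course fits within it. For the immediate follow-up, a control would have to complete the course within about 12 + 2 = 14 weeks of the start, so this route bears mainly on the 6-month assessment.

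**4. Size of the dilution (illustration; every input except 36 per arm is assumed).** Let δ be the true effect in SD units of the quantity analysed and c the share of controls who take the course and gain its full benefit. Compared as randomised, the expected difference is

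δ − cδ = (1 − c)δ.

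Power is that of a two-sided two-sample t-test at alpha 0.05 with 36 per arm (70 degrees of freedom) and noncentrality (1 − c)δ × √(36/2) = (1 − c)δ × 4.243. Take δ = 0.67, the value that gives 80% power at this size:

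| c | Controls exposed (of 36) | Difference (SD) | Noncentrality | Power |
|---|---|---|---|---|
| 0 | 0 | 0.67 | 2.84 | 80% |
| 10% | 3.6 | 0.60 | 2.56 | 71% |
| 20% | 7.2 | 0.54 | 2.27 | 61% |
| 30% | 10.8 | 0.47 | 1.99 | 50% |

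**5. Sensitivity to the assumed effect.** The normal approximation, Φ((1 − c)δ × 4.243 − 1.96), gives for c = 0, 10%, 20% and 30%:

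- δ = 0.5: 56%, 48%, 40%, 32%
- δ = 0.8: 92%, 86%, about 77%, 66%

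**6. Prior attendees.** If a share p of both arms has already taken the course and gains nothing further, the difference becomes (1 − p)δ, the same form as above. With p = 10%, and c = 10% among the remaining controls, the factor is 0.9 × 0.9 = 0.81. At δ = 0.66, the normal-approximation effect for 80% power, the difference is 0.66 × 0.81 = 0.53 SD and power is about 62%.

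**The case against.** **Uptake is not shown.** The Telemental course is viewed at outpatient clinics, while the trial recruits through hospital flyers, the Neuropsychology Service, veterans' posts and Councils on Aging. No section says a control would be offered a place. At c = 30%, about 11 controls would have to take the course, and the Telemental portion plans only 20 research participants (not a stated cap on the course). This stands: the upper end of the range is a stress case, not a forecast.

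**The bias is conservative.** Earlier attendance is balanced in expectation by randomisation, and both routes work against finding a benefit. Section 2.3 also describes a pilot. This stands, and it limits the weight of the point. It does not remove the ambiguity of a null result.

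**The calculation is not the planned test.** It uses a t-test rather than the group-by-time ANOVA, and full benefit in every exposed control is generous. The shrinkage factor (1 − c) comes from the full-benefit assumption, not from the choice of test. Partial benefit would make it milder.

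**A reader might infer that Section 4.6.4 is simply false.** The documents do not go that far. The sentence is consent-style wording, and correcting it changes nothing in the comparison. Section 3.3(b)(ii) places the Telemental course among the study procedures and gives questionnaires to all veterans taking it, which can be read as making the course part of the study. The recruitment wording points the other way. The sections should be reconciled.

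**A reader might also infer that veterans are already taking the Telemental course, in the same year as the randomised enrolment.** Neither is established. Questionnaires are given before the course starts. Section 4.5 shows that a component was added after enrolment had begun, so matching references to the coming year do not date one portion against the other.

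**Unseen material.** The consent form and course outline are not in the documents and could contain a restriction.

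**Conclusion.** The gap in the rules is real. As written, veterans who have had the course may enter either arm, controls may take the Telemental version before the 6-month assessment, and nothing listed records either. Any such exposure that carries benefit would dilute the contrast toward no effect.

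The size is unknown. A loss from 80% power to between 71% and 50% depends on an assumed 0.67 SD effect, alpha of 0.05, uptake of 10% to 30%, and full benefit in exposed controls. None of these comes from the documents.

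It would be too strong to conclude that the comparison is contaminated. The documents do not show that any control took the course or that any earlier attendee was enrolled. They do not say whether the on-site clinical group continues during the trial. The concurrent route therefore rests on the Telemental version alone, whose timing relative to randomised enrolment is not given. This is a cheap improvement to the plan, not a statement that is wrong as written.

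**What to change.** 1. **Section 4.4(a):** add that a veteran who has taken, or is enrolled in, any AgeWISE course, clinical or Telemental, is not eligible for the randomised comparison.
2. **Sections 3.3 and 3.4:** at each follow-up, ask every randomised veteran, in both arms, whether they attended AgeWISE sessions outside their assignment.
3. **Section 3.5:** keep the as-randomised comparison primary. Report the number exposed by arm and visit, and specify a sensitivity analysis that allows for exposure. Simply dropping exposed controls would break the randomisation, so that should not be the only one.
4. **Minor:** reconcile Section 4.6.4 with Sections 3.3(b)(ii) and 4.5 by stating whether the Telemental course can be taken without joining the research.

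The cost is one eligibility line, one question per follow-up visit, a short addition to the analysis plan and one clarified sentence. A few interested veterans become ineligible. The question records crossover but does not prevent it.

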#### **4.7 Costs and Payments**

Bedford AgeWISE: Veterans will be paid \$10 an hour for their time. Assessments at baseline, initial follow-up, and 6-month follow-up are expected to take an estimated 4 hours each. Therefore, veterans will be paid a total of \$40 per assessment, or \$120 over the course of the study. In addition, if veterans have a study partner, the study partner will receive \$10 for 1 hour at each of the 3 assessments (study partner time estimated to be one hour per assessment), for a total of \$30 over the course of the study.

Qualitative Interview: Veteran and Non-Veteran participants will be paid \$10 an hour for their time. Interviews will last approximately 1.5 hours. Therefore, participants will be paid a total of \$15 dollars for their time. If the interview lasts longer than 1.5 hours, participants will continue to be paid at a rate of \$10 per hour.

Telemental Health Group: Veterans will be paid \$10 dollars an hour for their time. Assessments at baseline and immediate follow-up, are expected to take two hours each. Therefore, veterans will be paid a total of \$20 per assessment or \$40 over the course of the study.

